**Program Development: I-ANBL**

We anticipate four primary components to the program, which will be designed by our focus group participants, CAB members, and Native team members, including: the I-ANBL Interactive website, an educational curriculum, pharmacotherapy, and participant incentives, all of which will be tailored to a heterogeneous group of AI tribal college students.

***I-ANBL Interactive Individual Sessions***

In order to deliver personalized and individually-tailored intervention, we will include three inter-related components: 1) a web screening instrument to measure demographics, health status, smoking status, health behaviors, behavioral determinants, and level of motivation and confidence, 2) a message source file that contains all tailoring messages and a, 3) computer program that offers the possibility to analyze the screening results and to select the correct message from the message source file.

Development of the Internet site will be led by [name], programmer at KUMC with whom we have worked on several projects and who developed the current ANBL

([www.anbl.org](http://www.anbl.org)), CAICH ([www.caich.org](http://www.caich.org)), and AIHREA ([www.aihrea.com](http://www.aihrea.com)) websites. We will follow all guidelines for the development of Internet sites for the AI/AN population set forth by the Office of Disease Prevention and Health Promotion discussed in the background section. We will also follow all guidelines set forth by our focus group participants and our CABs.

Programming will be done using the Adobe Creative Suite® and Moodle CMS™. These are software programs designed to assist in the development of Internet sites with which the PI and web designer have experience. The website will have a patient portal that participants will log into. All participants will have an individual section in their portal in which they will enter survey data and can request private on-line chats with our research assistants. Participants will not have access to anyone else's information nor any personal information from an individual.

Computer expert system feedback reports will be based on participants' responses to survey data and include information on: 1) current stage of motivational readiness for smoking cessation; 2) increasing self-efficacy (i.e., confidence) for remaining smoke free; 3) cognitive and behavioral strategies associated with abstinence (processes of change); 4) how the student compares to prior responses (progress feedback); 5)

How the student compares to individuals who are abstinent (normative feedback); 6) maintenance of smoking abstinence. The computer expert system will draw from a bank of several hundred messages addressing different levels of cultural, psychosocial, and environmental factors affecting smoking cessation. Intervention participants will also receive tip sheets addressing barriers specific to American Indian smokers and quitting (as identified during our formative research and Phase 1 of the study).

**Educational Curriculum:** We will adapt the ANBL materials for the tribal college population through the planned focus groups in Phase I of this study. Previous participants in formative research have stressed that cultural issues must be ingrained within the program and its accompanying education materials, not given "lip service" by putting pictures of AI people on otherwise "white" materials. We will continue to follow this guideline as we modify the materials. We will begin our educational materials modification with our current educational materials for ANBL (*see appendix*). Topics will be modified based on student input.

**Pharmacotherapy:** Pharmacotherapy is recommended for smokers trying to quit. We plan to give participants in our cessation program a choice of varenicline, bupropion, nicotine replacement therapy or no pharmacotherapy. We choose to give our participants a choice because our experience shows that we would be unlikely to recruit AI participants into a trial that requires pharmacotherapy use. Many AI are unwilling to use Western pharmacotherapy at all and others are unwilling to participate in a "drug trial", particularly if randomization is involved. All participants requesting pharmacotherapy must be medically cleared prior to receiving it.

The prescription medications (Chantix and Bupropion) and over-the-counter NRT (patch, gum, and lozenge) will be stored at KUMC in locked cabinets. KUMC will be responsible for mailing requested medications to the Polson Tribal Clinic in Polson, MT. After getting medical clearance from on-the-ground physician, participants will pick up a one month supply of study medication at the clinic. All the participants will be monitored weekly via web based system for any potential adverse events.

**Participant Incentives:** Incentives will be identified by focus group participants, CAB members, and Native research team members. For ANBL, we have used things like quit kits (hard candy, toothpicks, etc.), stress balls, flute music CD’s for relaxation, and Rez-robics® (aerobic dance videos that include pow wow and traditional dance), among other things. We will provide participants with gift cards for participating in the research. At baseline, we will give participants \$20 gift cards for survey participation. At 12-weeks and 6-months, we will give participants \$40 gift cards for survey participation. We will also give participants a \$10 gift card for providing saliva for cotinine analysis at the time points above. In addition to the above incentives, participants will also receive a \$10 gift card if they complete at least 5 of the weekly web sessions. If the participants complete all 8 weekly web sessions they will receive a \$20 gift certificate. All participants will be asked to provide saliva at baseline, 12-weeks, and 6-months. We ask for repeat samples from all participants for two reasons: (1) nicotine metabolism of smoking has not been previously examined and we plan to look at decreases in use, as well as quitting; and (2) we do not want some participants to be able to obtain additional incentives because we do not want to bias our results. We do not anticipate a problem with participants’ willingness to provide saliva; our ANBL programs have a 100% participation rate in this, even though it is voluntary for participants to provide saliva.

**Anticipated Flow of Participants:**

Telephone Eligibility Screening Interview		
↓		
In-Person Randomization Visit (n=300)		
←      ↓      →		
Web-based weekly		
Sessions	I – ANBL (n=150)	I – FV (n=150)
1	Preparing to quit, pharmacotherapy/nrt, why do people smoke	Assessment of Risk for Heart Disease, pharmacotherapy/nrt
2	Cigarette smoking and Native people, Quit smoking date	Increasing fruit and vegetable consumption, Quit smoking date
3	Coping with Withdrawal	Physical activity
4	Traditional use of tobacco	High blood pressure
5	Stress reduction and relaxation techniques, traditional meditation techniques	Salt and sodium intake
6	Weight management, Healthy American Indian foods, exercise	High Cholesterol
7	Friends and family and quitting smoking, social support	Maintaining healthy weight
8	Staying quit – congratulations Long term maintenance	Low cost healthy eating – fruits and vegetables
Email reminders will be sent before each session so that participants will log in at the appropriate time		
12	End of pharmacotherapy treatment, feedback of program	End of program, feedback

Email reminders will be sent before each session so that participants will log in at the appropriate time		
Month 6	Assessment for current smoking status	Assessment of current smoking status

(Detailed descriptions of the weekly I-ANBL web materials are included in the appendix: will be adapted to integrate tribal college student issues identified during Phase 1 of the study)

- Telephone Screening Intake:** Research Assistants will review inclusion/exclusion criteria, smoking status and basic information about the program. We will not exclude participants who use other forms of recreational tobacco (eg – smokeless tobacco) because, based on our preliminary data, we would be excluding eligible participants if we did so. In addition, community members have encouraged us to be more inclusive for acceptability of the research in the community and make the inclusion criteria less restrictive. Therefore, we will examine use of other tobacco products in a secondary analysis. We estimate screening intake to take 10-15 minutes.
- Individual In-Person Visit (Randomization):** Potential participants will meet with a research assistant on campus. At this initial in-person visit, the research assistant will have randomization assignments with them so they can inform the participant which arm they have been randomized to for this program. This session will allow research assistants to explain the program and answer any questions the participant may have that he or she may have about the program. Informed consent will also be obtained during this visit. Finally, it allows the research assistant to explain NRT or pharmacotherapy and provide each participant with information. Individuals who consent to participation will be enrolled in the program and will remain in the arm to which he/she is randomized to for the study. Research assistants will collect baseline saliva sample from each participant. Participants will be informed for future samples (week 12 and month 6), we will request mailings of saliva samples so they will be taught how to provide such samples at this baseline visit. Saliva sample kits will be provided via overnight mail with a pre-paid overnight return. Members of our team have used this approach in other phone-based smoking cessation programs with success. Participants will be asked to make a decision about NRT or pharmacotherapy prior to the second web session. Facilitators will answer any questions the participant has and participants will be given the option of having the study physician call them to discuss personal concerns. Estimated time for individual session is 50-60 minutes. Participants who have not yet decided on medication will be asked to do so then. All participants requesting any form of pharmacotherapy will complete the corresponding medical screener. The study physician will review all medical information prior to the first session. After taking part in the initial session, participants will be e-mailed a login to the website prior to their first session. Future surveys will be done via web interface.
- Internet Session 1:** Participants will be asked to log into the website prior to the first session to allow for any problems with the site to be fixed prior to sessions starting. Participants who decide to take any study medication will need to visit the Polson Tribal Clinic in Polson, MT to pick up a one month supply of study medication. Any unused NRT or medication will be dropped off at the clinic and then mailed back to the research assistants by the clinic staff. The study physician will be available to answer additional

questions. Beginning with this session and continuing through all sessions. Topics we anticipate covering include, but are not limited to: preparing to quit, dealing with cravings, support systems, traditional tobacco, stress reduction, weight management, and staying quit, along with other topics determined during program development. For each session, the tribal college student will begin the session by answering a series of questions to produce an individually-tailored report that will be provided on the screen at the end of each week's session so that the smoker can work on strategies during the week before the next internet session. Estimated time for the web session is 30 minutes.

- **Internet Sessions 2-8:** *The second session is the quit date for all participants in the group.* Weekly procedures will follow the same format as for the first session. At the session dealing with traditional tobacco, participants will be asked to talk about their own use, though they will not be required to do so because this is not always culturally appropriate. Participants will be asked to fill out weekly brief surveys about their use of tobacco during the week; e-mail reminders will be sent. Participants will also be asked to fill out brief session evaluations on-line after each session; e-mail reminders will be sent for these as well. Session evaluations will go directly into a separate database that will be de-identified; participants will be told about this database to encourage more truthful responses.
- **Weeks 9-11:** Participants will receive one individual email per week from a research assistant.
- **Final Session- End of Treatment (Week 12):** Session content procedures will follow the same format as for other sessions. All participants, regardless of smoking status will receive a certificate of achievement for completing the program and will be asked to submit a saliva sample.
- **6-Month Follow-Up:** At 6-months post-baseline, participants are asked to take part in a final internet session and will receive a \$20 gift card for participation. They will be asked about their smoking status and will be asked to submit a saliva sample. Participants who do not report abstinence from smoking use will be asked if they would like to participate in the full program again. If they choose to participate a second time, they will not be included in *study outcome* measures, though we will track their success. This is done to mimic the real-world situation where a program could be repeated. After the 6-month follow-up, participants will be sent a final anonymous survey about the program via e-mail.

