## **V. Study Procedures**

### **Design Overview**

The proposed study is a randomized design in which Tribal College smokers will receive one of two internet-based interventions: 1) a culturally and individually tailored, interactive smoking cessation intervention (**I-ANBL**); or 2) internet-based healthy diet -fruit and vegetable consumption intervention (**I-FV**). Participants in both groups (I-ANBL and I-FV) will be offered pharmacotherapy (e.g. varenicline or bupropion or NRT). The primary outcome of interest will be biochemically verified continuous abstinence at 6 months. Secondary endpoints include number of quit attempts and number of cigarettes smoked (among continuing smokers), pharmacotherapy utilization, and the number of completed web-sessions. We will also examine the marginal cost-effectiveness of the intervention.

We propose the adaptation and testing of a culturally tailored smoking cessation program for tribal college students. We will finish developing the program using an iterative, CBPR process that we have used in the past to develop a successful smoking cessation program for AI.

The study will be done in three phases over a five-year period. Phase 1 will include adaptation of the program and tailored materials, including assessments of the website for scientific

accuracy, readability, cultural appropriateness, and navigability; Phase 2 will be to conduct the randomized trial and Phase 3 will consist of data analysis and dissemination.

Participants will be recruited from a Tribal college.

**Pharmacotherapy:** The PI of this study along with our AI community members agreed that all participants (I-ANBL and I-FV arms) had to be offered pharmacotherapy (varenicline or bupropion or NRT) as a component of the study design. This decision was a collaborative one between the AI tribes and the investigators who have worked with this population. The AI community will not accept placebo treatment, therefore, the interventions would not be acceptable or feasible to potential participants if a placebo was part of the study design.

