**Implementation Plan**

The project will be implemented in three phases over five years, as summarized in the table. The main purpose of this study is to determine the effectiveness of an internet-based culturally-tailored smoking cessation program for tribal college smokers.

Phase 1: Development and Training	Development and assessment of interactive website; training of staff; focus groups and pre-testing, conduct meetings with CAB, submit any protocol modifications for community and IRB approval	Year 1
Phase 2: Deliver Intervention	Recruitment of tribal college smokers into study, baseline measurements, randomization of eligible students, implementation of internet-based intervention, follow-up, preliminary data cleaning, and initial data analysis	Year 2 – Year 4
Phase 3: Data analysis and dissemination	Post-intervention assessments; final data cleaning and analysis; manuscript preparation; presentations to communities and at professional conferences	Year 5

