### Phase 3: Data Analysis and Dissemination

The objectives of this phase are 1) to conduct data analysis and 2) to disseminate the program.

In Year 5, we will complete post-intervention assessments, data analyses and report writing.

Process and outcome data will be presented at scientific conferences and manuscripts will be submitted to peer-reviewed scientific journals. Ultimately, we envision that **I-ANBL**, if efficacious, could be disseminated and

used as a culturally tailored smoking cessation intervention that could be adopted across different tribal colleges.

**Sample Size and Power:** The primary endpoint will be cotinine verified 7-day point prevalence abstinence at Month 6. Per preliminary findings, we expect a 30% cessation rate in the **I-ANBL** arm and a 15% cessation rate in the **I-FV** arm. Using the chi-square test, and the assumptions above, 121 participants in each group will give us 80% power to detect this difference with a type I error rate of 5%.

Given retention rates from our earlier studies, we expect attrition rates to be approximately 20% over the 6 month study period. Therefore, we anticipate needing to enroll 300 participants at baseline in order to have 242 active participants at 6 months.

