### **Primary Aim/Hypotheses:**

1. To test the effectiveness of the **I-ANBL** compared to the **I-FV** on smoking cessation among tribal college smokers.

Hypothesis 1: At 6 months, participants in the **I-ANBL** group will show higher 7-day point prevalence abstinence rates than those in the **I-FV** group.

We will compare the salivary cotinine verified prevalence abstinence rates at 6 months between the two groups using logistic regression. For our primary comparison, we will conduct per-protocol analyses on (a) only the participants who complete the study, as well as intent-to-treat analyses on (b) all subjects by imputing the dropouts as smokers and (c) all subjects by using the Markov Chain Monte Carlo (MCMC) imputation technique. In (c), the missing data related to attrition can be reasonably assumed to be missing due to known characteristics of our database (i.e., missing at random). We will create a large number of (e.g., 200) complete datasets via expectation-maximization algorithm as prior estimates for the MCMC procedure; and then combine the analysis outcomes from each complete dataset to make valid statistical inferences. To evaluate secondary endpoint, we will compare the salivary cotinine verified prevalence abstinence rates between the groups at Week 12 (end of pharmacotherapy). Finally, as we have no preliminary estimates of relapse based upon timeline follow-back, we will conduct explanatory, failure analyses to compare the time to relapse between the groups. We will calculate failure function (cumulative probability of smoking cessation as a function of time) and fit Cox regression models to the 6-month self-report data on smoking status.

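### The recruiter carries the assignments to the enrolment visit to tell candidates their arm; consent and baseline are not put first and no concealment is described, so who enrols can depend on the arm

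*Protocol*

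**What the plan says.** The visit is described in the protocol, section V, under Anticipated Flow of Participants, in the item on the individual in-person visit (randomization). The text runs in this order:

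1. "Potential participants will meet with a research assistant on campus".
2. At that visit "the research assistant will have randomization assignments with them so they can inform the participant which arm they have been randomized to".
3. The research assistant explains the program and answers questions.
4. Informed consent is said to be obtained at the same visit, with no position given relative to step 2.
5. "Individuals who consent to participation will be enrolled in the program and will remain in the arm to which he/she is randomized to".
6. The baseline saliva sample is collected.

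The item on telephone screening, just before, has research assistants review eligibility. The same staff role therefore screens, explains the study and carries the assignments.

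The Phase 2 row of the Implementation Plan table gives a different order: "baseline measurements, randomization of eligible students, implementation of internet-based intervention". The objectives under Phase 2: Delivery of Interventions also go from recruiting and screening to randomizing to implementing. Neither place mentions consent or says who holds the assignments. No envelope, central or web release, independent list holder or other concealment step appears anywhere in the protocol.

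**The concern.** Randomization makes the arms comparable only if the decision to enter a person is made without knowledge of that person's assignment. Here the person at the visit is a candidate, the assignment is spoken of as already made, and the person who recruits is the one who carries it. Two routes to selection are open:

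- The candidate hears the arm and then decides whether to consent.
- The recruiter, if able to read the assignment beforehand, presses or eases off according to the arm and the candidate.

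The arms look different to a smoker. I-ANBL is an individually tailored cessation program. I-FV is a heart-health program with its smoking content removed and no individual tailoring. Someone who came forward to quit has a reason to prefer the first.

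Selection at this point changes the mix of the arms before any baseline value is recorded. The primary aim plans a completer analysis, "intent-to-treat analyses on (b) all subjects by imputing the dropouts as smokers", and a multiple-imputation analysis. All three work on people who entered the study. Someone who declined on hearing the arm has no record to impute, so the loss cannot be detected or corrected afterwards.

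**Working it through.** **The protocol's own figure.** Sample Size and Power expects 30% v 15% abstinence, with 80% power and 5% type I error. The two-sided test of two proportions without continuity correction needs

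n = [1.96 × √(2 × 0.225 × 0.775) + 0.842 × √(0.30 × 0.70 + 0.15 × 0.85)]² / 0.15² = 120.5, so 121 per arm.

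This agrees with the protocol, and power at 121 is 80.2%. The sample size is sound and is not at issue. It presumes arms that differ only by treatment.

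**Reading the text.** The claim depends on order and custody, so the places are set side by side.

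| Place in section V | Consent | Baseline | Arm made known | Holder of assignments |
|---|---|---|---|---|
| In-person visit (randomization) | same visit, mentioned after disclosure | saliva, mentioned after consent | first activity described | research assistant |
| Implementation Plan, Phase 2 row | not mentioned | before randomization | not mentioned | not mentioned |
| Phase 2: Delivery of Interventions | not mentioned | not mentioned | not mentioned | not mentioned |

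The operational text, which staff would follow, does not put consent and baseline first. The two summaries do not supply what it lacks.

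**How large could it be?** Nothing in the protocol gives the share of candidates who would refuse an arm, so the following is an illustration. Assumptions:

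- There is no true treatment effect.
- Half of candidates are motivated and quit at 25%; half are less motivated and quit at 5%. These rates are chosen so that the mean is 15%, the protocol's I-FV rate.
- A fraction d of motivated candidates decline on hearing I-FV. Nobody declines I-ANBL.

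Among those who enrol in I-FV the motivated share is (1 − d)/(2 − d), so

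I-FV rate = 5% + 20% × (1 − d)/(2 − d), against 15.0% in I-ANBL.

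For d = 0.3: 5% + 20% × 0.7/1.7 = 13.24%, a gap of 1.76 points. The rejection rate of a two-sided 5% test uses the pooled standard error for the critical value and the unpooled one for the spread. At 121 per arm both are about 0.0448, so

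Φ(0.0176/0.0448 − 1.96) + Φ(−0.0176/0.0448 − 1.96) = 6.8%.

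| d | I-FV rate | Gap (points) | Rejection, 121 per arm | Rejection, 150 per arm |
|---|---|---|---|---|
| 0 | 15.00% | 0 | 5.0% | 5.0% |
| 0.1 | 14.47% | 0.53 | 5.2% | 5.2% |
| 0.2 | 13.89% | 1.11 | 5.7% | 5.9% |
| 0.3 | 13.24% | 1.76 | 6.8% | 7.2% |

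If the less motivated decline I-FV instead, the gaps become −0.53, −1.11 and −1.76 points, with rejection of 5.1%, 5.7% and 6.6% at 121 per arm.

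**A stronger case**, for scale only and with no support in the protocol: quit rates of 25% and 10%, consent of 60% (motivated) and 40% (less motivated) in I-ANBL, and 40% and 60% in I-FV. The rates are 0.6 × 25% + 0.4 × 10% = 19.0% and 0.4 × 25% + 0.6 × 10% = 16.0%. The gap is 3.0 points, with rejection of 9.4% at 121 and 10.5% at 150 per arm.

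**The case against.** The strongest reply is that the visit item is silent on order and does not state a wrong one. It can be read as a list of what happens in a single visit. The Phase 2 summaries fit the usual sequence, and carrying assignments to the visit is compatible with carrying sealed envelopes.

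The room for refusal is also narrowed. Willingness to take part in all study components and to be followed for 6 months is an inclusion criterion, and eligibility and basic program information are covered by telephone beforehand. Gift cards are described without distinction by arm. "Participants in both groups (I-ANBL and I-FV) will be offered pharmacotherapy", and "The second session is the quit date for all participants in the group", with the session table showing a quit date in both arms.

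Finally, the illustrated gaps of 0.5 to 1.8 points are small beside the planned 15-point difference, their sign is unknown, and every behavioural input is assumed.

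Much of this is fair. The motive to decline I-FV is weakened, and the computed magnitude is not what carries the point. But the protocol calls those attending potential participants, speaks of randomization as already done and mentions consent only after disclosure, so the adverse reading is the natural one. The willingness criteria limit arm-dependent refusal without excluding it. Sealed envelopes are not ruled out, but nothing requires them. The SAP is not at hand, but custody of the assignments and the order of the visit are matters of conduct that belong in the protocol.

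**Conclusion.** The concern holds. As written, a research assistant may tell a candidate the arm before consent and baseline, and no described safeguard keeps the assignment from the recruiter. Whether such selection would occur, how large it would be and which arm it would favour cannot be learned from the protocol. Under the moderate assumptions above the false difference is 0.5 to 1.8 points in either direction, with type I error up to 6.8% at 121 per arm. The stronger, unsupported case gives 3.0 points and 9.4%.

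The weight of the point rests on principle and not on these figures. The defect affects the primary comparison, could not be measured from the trial's data and could not be repaired by any of the planned analyses. It should be corrected before enrolment.

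**What to change.** In the item on the in-person visit, state the order: confirm eligibility, obtain informed consent, collect the baseline survey and saliva, then reveal the next assignment. Say that it comes from a source the recruiter cannot see in advance, either sequentially numbered sealed opaque envelopes prepared by someone outside recruitment or release through the REDCap system already used for data. Bring the Implementation Plan table into line by placing consent before baseline and randomization. Everyone randomized after consent then counts in the intent-to-treat analyses. If the SAP already defines the set that way, no change is needed there.

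The cost is protocol and procedure wording plus envelopes or a REDCap set-up, with no added visit and no added participants. The drawback is that some people may withdraw on learning their arm after they have been randomized. They would stay in the denominator and count as smokers in the dropouts-as-smokers analysis. That loss is visible and can be reported by arm, whereas refusals before enrolment cannot.
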